**Table 7-3. Biological matrices for analyses**

	Blood Samples			Vaginal, Rectosigmoid, and Semen Samples			
	Serum	PBMC	CD4+ blood cells	Total tissue cells	CD4+ tissue cells	Luminal fluid & semen	Homogenate
TFV-DP		X	X	X	X		X
FTC-TP		X	X	X	X		X
TFV	X					X	X
FTC	X					X	X

Descriptive statistics, such as means, medians, variance, and interquartile ranges, will be used to summarize Day 35 pre-dose concentration ( $C_t$ ) by gender and by dose arm. Simple comparison of median concentration level between dose arms will be done with standard non-parametric methods. Gender- or dosing-specific CVs of Day 35 pre-dose concentration ( $C_t$ ) will be estimated. These CV estimates would be informative to the future studies even if dose proportionality does not hold.

### 7.6.1.2 Intra-Participant Variability

Intra-participant variability will be described by the coefficient of variation of concentrations assessed on Day 28 and Day 35, which are assumed to be at steady-state, using data from all evaluable participants across dosing arms. We will confirm that steady-state was achieved by evaluating drug concentration data from Day 7, 14, and 21. If the dose-proportionality is established as described earlier, then dose-adjusted concentrations will be used for a more robust assessment. These variability estimates will be calculated for all analytes in blood and blood cells. As supportive evidence, the accumulation data from Day 7, 14, and 21 will also be used to estimate the elimination rate constant. Tissue and luminal assessments cannot be calculated due to the absence of multiple steady-state samples.

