### 1.1.6 Importance of Intra-individual Variability

Knowledge of intra-individual variability in drug concentrations is necessary to determine accurate sample size estimates for studies that plan to use drug concentration monitoring as an adherence measure. Without this parameter, estimates can be made from inter-individual variability from existing unpaired studies. However, the inter-individual approach typically results in overestimates of variability and hence a larger than necessary sample size. Alternatively, some conservative assumptions can be made for intra-participant correlation, though this introduces an additional variable that may cause estimates to be either too high or too low.

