## **1.2 Rationale**

### **1.2.1 Overall Study Rationale**

This PK study is designed to establish the dose-proportionality of TFV and FTC (serum and intracellular forms) with daily to weekly dosing. This information is essential to (1) employ drug concentration as an adherence measure in future PrEP studies, and (2) to estimate the anticipated concentration of parent and active moieties of TFV and FTC in intermittent PrEP regimens associated with full adherence to a prescribed regimen. In addition, intra-individual variability will be assessed to improve sample size estimates in future PrEP studies that use drug concentration as an adherence measure or where PK-PD correlations are planned. The dose-proportionality of intra-cellular phosphates of the two components of the study product has not previously been established. Given the complexity of movement of these drugs between body compartments (central compartment, vaginal mucosal tissue, vaginal lumen, gastrointestinal mucosal tissue, gastrointestinal lumen), into cells within these compartments, and intra-cellular phosphorylation, it is possible that non-dose proportional kinetics, such as mixed or zero-order saturable processes may be operating.

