### 1.2.3 Dosing Duration Rationale

Dose-proportionality can be assessed at any point of observation following initiation of dosing. Intra-individual variability, however, can best be assessed at two sampling times not anticipated to vary based on PK principles. Essentially, by definition, this condition is achieved when steady-state has been reached. This study requires direct observation of dosing to rule out adherence as a cause for variation in drug concentrations. Therefore, we plan to begin sampling for intra-individual variability assessments as early as possible after dosing, balancing logistical difficulties (up to daily dosing for study staff and research participants) and PK limitations. Intracellular TFV-DP concentrations are estimated to achieve between 93% and 97% of steady-state Cmin (trough) concentrations after 4 half-lives and 5 half-lives, respectively, have elapsed after initiation of Truvada® dosing. Based on an estimated 150-hour TFV-DP intracellular half-life (FTC-TP will achieve steady-state earlier, given its far shorter 36-hour half-life), the 4 and 5 half-life points coincide with 28 and 35 days of dosing. Laboratory assay variation for all of the assays planned for this study are more than twice as large as the very small 4% difference in concentrations that we expect to measure between Day 28 and Day 35. Accordingly, we plan to dose for 35 days, and to use samples from Day 28 and Day 35 for our intra-individual variability estimates. One could argue for longer periods of dosing to further reduce differences between doses in the asymptomatic approach to a true steady-state, but we believe that our proposed plan provides a reasonable balance between logistical complexity (daily dosing under direct observation) and reasonable experimental variation.

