## 7.3 Accrual, Follow-up, Retention, and Sample Size

A total of 32 evaluable men and women will be enrolled over a period of approximately 6 months at multiple sites. An equal number of participants (8 per arm) will be randomized into each of the four dosing arms. Each enrolled participant will be followed for 7 weeks.

Research participants may miss one of the following pre-steady-state study visits when on drug (Day 7, Day 14, Day 21) and remain in the study and remain eligible for evaluation in the PK outcome analysis of the study. Day 0, Day 28, Day 35, and Day 49 are required for a participant to be considered evaluable. Optimally, all study product dosing will occur on the date prescribed. However, some forgiveness of strict adherence to the schedule will be tolerated as long as the total dose within each week is consistent with the prescribed total. Therefore, for arms 1, 2, and 3, study drug dosing can be delayed by 2 days, during the first 3 weeks of the study. Thereafter, all doses in week 4 and 5 must be taken as scheduled. In Arm 4, all doses for research participants must be taken as scheduled. Failure to comply with these scheduled requirements will result in discontinuation from the study after a final safety evaluation.

Evaluable participants are expected to represent 95% of participants enrolled into the study. No adjustments are made for retention losses since all discontinued or inevaluable participants will be replaced. Each study site will establish participant retention procedures to target lost-to-follow-up rates of <5% in order to minimize additional enrollments to compensate for inevaluable participants.

For the intensive cohort, a subject must have all blood on Days 0, 28, 35 and 49, and vaginal, seminal, and rectal samples on Days 35, and 49 to be evaluable. If the subject is inevaluable for

the intensive cohort, but has met evaluability criteria for the non-intensive cohort AND there is an opening in the non-intensive arm-gender cohort matching the subject, then they may be switched in assignment to the non-intensive cohort. If the intensive subject fails to complete all required samples OR there is not an opening consistent with their gender/arm, then the participant is discontinued after the final safety evaluation. In either case, the subject needs to be replaced in the intensive sampling group.

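### Neither direct reading of the Day 28/Day 35 coefficient of variation in Section 7.6.1.2 estimates the within-person CV that the second primary objective needs

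*Protocol*

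**What the plan says.** Describing intra-individual variability of the intracellular analytes at steady state is the second of two primary objectives (Protocol Section 2.1). Section 1.2.3 fixes the data as two samples per person; the plan is "to use samples from Day 28 and Day 35 for our intra-individual variability estimates". Section 7.6.1.2 names the statistic: "Intra-participant variability will be described by the coefficient of variation of concentrations assessed on Day 28 and Day 35", obtained "using data from all evaluable participants across dosing arms". If dose proportionality is established, "then dose-adjusted concentrations will be used for a more robust assessment". The section covers all analytes in blood and blood cells. It gives no rule for turning 32 pairs of values into one estimate.

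The purpose is stated twice. Section 1.1.6: "Knowledge of intra-individual variability in drug concentrations is necessary to determine accurate sample size estimates for studies that plan to use drug concentration monitoring". Section 1.2.1: "intra-individual variability will be assessed to improve sample size estimates in future PrEP studies". Section 1.1.6 also warns that relying on inter-individual variability usually overstates variability and so makes studies larger than they need to be.

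The protocol gives no expected within-person CV and no precision target for this objective.

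**The concern.** With two values per person, each individual CV rests on one degree of freedom. Such a CV is skewed and, on average, too small. Averaging many of them reduces the noise but leaves the bias. The other direct reading, one CV over everybody's values, measures a different quantity, because differences between people enter it. That is the contamination Section 1.1.6 wants to avoid.

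At stake is the usefulness of a primary result. Where within-person variability drives a design, sample size scales roughly with the square of the CV. A CV that is too low leads to underpowered later studies, and one that is too high to wastefully large ones.

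**Working it through.** **Inputs**

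- Two steady-state values per person, Days 28 and 35 (Sections 1.2.3 and 7.6.1.2).
- 32 participants (Section 7.3: "A total of 32 evaluable men and women will be enrolled").
- Between-person CV of 25-35%, the planning range in Section 7.3.
- Expected drift: Section 1.2.3 puts the two days at 93% and 97% of steady state, so 0.97/0.93 = 1.043. The protocol calls this a "very small 4% difference in concentrations that we expect to measure between Day 28 and Day 35".
- True within-person CV: not given, so assumed values of 10% to 45% are used.

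The plan has no figure of its own to reproduce here.

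**Reading 1: a CV per person, then a mean or median**

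The SD of two values is |x1 - x2|/√2. For normal data this is σ|Z|, with Z standard normal. Its mean is σ√(2/π) = 0.798σ and its median is 0.674σ. The CV also divides by the person's own mean, so the full ratio was simulated with 2,000,000 pairs per setting and no drift. Entries are estimate ÷ true CV:

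| True CV | Mean of CVs, lognormal | Median of CVs, lognormal | Root-mean-square of CVs, lognormal | Pooled log-scale variance, lognormal | Mean of CVs, normal |
|---|---|---|---|---|---|
| 10% | 0.793 | 0.672 | 0.993 | 1.000 | 0.802 |
| 20% | 0.780 | 0.666 | 0.972 | 1.000 | 0.815 |
| 30% | 0.760 | 0.656 | 0.941 | 1.001 | 0.836 |
| 35% | 0.748 | 0.650 | 0.922 | 1.000 | 0.842 |
| 45% | 0.720 | 0.635 | 0.881 | 1.000 | 0.825 |

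With only 32 people and lognormal data, the mean and median ratios are 0.78 and 0.67 at a true CV of 20%, and 0.75 and 0.66 at 35%. The bias therefore does not depend on the number of participants. A drift of 4.3% changes the lognormal mean ratio little: to 0.83 at a CV of 10% and 0.75 at 35%.

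**Reading 2: one CV over all dose-adjusted values**

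For lognormal components, CV²(total) = (1 + CV²(between))(1 + CV²(within)) - 1. With an assumed within-person CV of 15%:

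- Between-person CV 35%: √(1.1225 × 1.0225 - 1) = √0.1478 = 38%, and 0.384/0.15 = 2.6 times the target.
- Between-person CV 25%: √(1.0625 × 1.0225 - 1) = √0.0864 = 29%, and 0.294/0.15 = 2.0 times the target.

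If the 35% already contains within-person variation, this reading returns about 35%, or 0.35/0.15 = 2.3 times the target.

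**Effect on a later sample size**

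This assumes that within-person variability alone drives the design and that the estimate is used unmodified. A CV at 0.80, 0.75 or 0.67 of the truth gives 0.80² = 0.64, 0.75² = 0.56 or 0.67² = 0.45 of the required n. As an illustration, take a true CV of 30%, a 1.25-fold difference, two-sided 5% and 80% power. Then 28 per group are needed. The understated CVs would give 18, 16 or 13 per group, with true power of 63%, 58% or 49%. In the other direction, a CV of 38.4% against 15% inflates n by 2.56² = 6.6.

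**The alternative**

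The pooled log-scale within-person estimator gives a ratio of 1.00 for lognormal data and 0.99 with 32 people. If drift is not removed, a 4.3% shift raises it to 1.045 at a true CV of 10% and 1.004 at 35%. If the data are really normal it runs high: 1.02 at a CV of 10%, 1.07 at 20% and 1.32 at 35%.

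**The case against.** The strongest objection is that the protocol never orders individual CVs to be averaged. A reader might infer from the two-point bias that the plan is committed to an understated CV and that later trials will be too small. The text does not support that. Section 7.6.2.1 says explicitly that half-lives are estimated per participant and then summarised; Section 7.6.1.2 says nothing similar. Dividing both of a person's values by the same dose leaves that person's CV unchanged, so the dose-adjustment sentence has an effect only if values are combined across people. That points away from averaged personal CVs. This part of the objection stands: the downward direction is not established.

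A second objection is that the combining formula belongs in a statistical analysis plan, which was not available and may settle the matter. The absence of a formula alone would indeed be no finding. But the protocol does name the statistic for a primary objective, and both direct readings of that statistic miss the target, in opposite directions. The pooling that the dose-adjustment sentence suggests, if done literally as one CV, is the reading that adds between-person variance.

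Third, the size depends on the distribution. This also stands. The 21-25% figure is for lognormal data with a CV of 10-35%. The protocol's own power simulation uses normal data, for which the understatement is 16-20%. A root-mean-square of individual CVs would be only about 1-8% low for lognormal CVs of 10-35%.

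**Conclusion.** The point holds as a defect in how the estimator is specified, with no fixed direction. Averaged two-point CVs are about 21-25% low for lognormal data with a true CV of 10-35%, 28% low at 45%, and 16-20% low for normal data; a median is about a third low. One CV over all dose-adjusted values is too high, by a factor of about 2.0 to 2.6 for the protocol's between-person range of 25-35% and an assumed within-person CV of 15%. A pooled within-person variance on the log scale is essentially unbiased for lognormal data (ratio 0.99-1.00), and Section 7.6.1.2 does not name it.

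The within-person CVs used here are assumptions, because the protocol states none. The effect on later sample sizes also assumes that planners use the reported figure as it stands. The documents do not support saying that future studies will be underpowered; that follows only if a mean or median of individual CVs is what is reported.

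**What to change.** Replace the statistic in Section 7.6.1.2 with the within-participant variance on the log scale. For each analyte and blood matrix:

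- s_w² = Σ[ln(Day 35) - ln(Day 28)]² / (2n), with n degrees of freedom; or, so that the expected drift of about 4% is not counted as variability, the same sum with the mean log difference subtracted and 2(n - 1) as divisor, with n - 1 degrees of freedom.
- CV_w = √(exp(s_w²) - 1).
- A chi-square 95% CI. With 32 degrees of freedom this is 0.80 to 1.32 times s_w, with the limits then converted to the CV scale.

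State that neither a mean or median of individual CVs nor a single CV over all values will be used as the estimate. The log scale matches the power model already chosen for dose proportionality in Section 7.6.1.1. Because the estimator runs high if the data are closer to normal with a large CV, the log-scale assumption should be checked. Dose adjustment is not needed for this estimate when both days carry the same dose, because the dose cancels in the difference.

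The cost is a sentence or two. No new data, visits or participants are needed.

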### **1.1.5 Drug Concentration Simulation Models**

In computer simulation models, the “expected” drug concentration is based on the PK characteristics of the drug and the prescribed dosing regimen of the study. To facilitate these simulations, PK data are available from several reports in which TDF (Viread®) has been administered to human research participants. From these studies, one can make some estimates of the effective intracellular half-life for tenofovir diphosphate (TFV-DP), the active moiety of the drug, which appears to be approximately ~150 hours (Hawkins et al., 2005; Pruvost et al., 2005; Pruvost et al., 2009). From these studies, however, the inter-individual variability for half-life and peak concentration ( $C_{max}$ ) for TFV-DP is relatively large (coefficient of variation around 50% to 65%). Accordingly, the best parameter estimates for such a simulation come from

individual study participants. To avoid intensive, frequent PK sampling, which would be cumbersome in a large clinical trial, one can employ a combination of (1) population-based estimates from the studies like those cited above, and (2) data from a few samples from each individual in a prospective study. To remove variability in adherence in estimation of individual PK parameter estimates, samples collected from the individuals tested should follow an observed dose, thus insuring 100% adherence without variability. With an observed dose, the possibility of variable adherence affecting subsequent drug concentrations is removed. This leaves the following variables to consider: inter-individual PK variability, assay variability, and unknown sources of noise that may vary with time in the environment. Examples of simulations of proposed dosing strategies of TFV-DP in PBMCs (Figure 1-1) and TFV in blood serum (Figure 1-2) are shown below.

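### For TFV-DP, the stated steady-state check uses only Days 7, 14 and 21, when the drug is by the protocol's own half-life still accumulating

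*Protocol*

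**What the plan says.** Protocol section 7.6.1.2 describes intra-participant variability by the CV of Day 28 and Day 35 concentrations, "which are assumed to be at steady-state". It then sets the check: "We will confirm that steady-state was achieved by evaluating drug concentration data from Day 7, 14, and 21". Later in the same paragraph those three days are called accumulation data and are used to estimate the elimination rate constant.

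Section 7.3 labels Days 7, 14 and 21 as pre-steady-state visits and lets a participant miss one of them and stay evaluable.

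Section 1.2.3 gives the reasoning behind the assumption:

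- "Intracellular TFV-DP concentrations are estimated to achieve between 93% and 97% of steady-state" trough after 4 and 5 half-lives.
- "Based on an estimated 150-hour TFV-DP intracellular half-life", "the 4 and 5 half-life points coincide with 28 and 35 days of dosing".
- A "very small 4% difference in concentrations that we expect to measure between Day 28 and Day 35", judged acceptable because assay variation is more than twice as large.

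Section 1.1.5 puts the inter-individual CV of TFV-DP half-life and peak concentration, quoted together, at about 50% to 65%.

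**The concern.** A steady-state check has to look at the period in which the plateau is claimed. The sentence in 7.6.1.2 names only days before that period and leaves out the two days whose status is in question. For TFV-DP, data that behave exactly as the protocol expects would show clear rises from Day 7 to 14 and from Day 14 to 21. The check would then either appear to fail or be passed by judgement.

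What is at stake is the meaning of the within-person CV. If some participants are still accumulating between Days 28 and 35, their drift enters the CV as if it were random intra-individual variability. Section 1.1.6 wants that CV for sizing later adherence studies. TFV-DP is also the analyte whose half-life set the 35-day dosing period.

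**Working it through.** **Inputs.** Half-lives are 150 h for TFV-DP and 36 h for FTC-TP (section 1.2.3), and 17 h for serum TFV and 10 h for serum FTC (Table 1-1). The half-life CV is 50% to 65% (section 1.1.5). There are 32 participants, 8 per arm (section 7.3). The within-person CV is not given in the protocol; 20% is assumed below unless stated otherwise.

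**Formula.** With first-order accumulation, the trough as a fraction of steady state at time t is 1 - 2^(-t/half-life). Dose-by-dose superposition for weekly, twice-weekly (Days 0 and 3) and daily dosing gives the same fractions at whole weeks, so one row serves all arms.

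**The protocol's own figures.** Four half-lives give 1 - 2^-4 = 93.75% and five give 1 - 2^-5 = 96.9%, which matches the stated 93% and 97%. The calendar mapping is approximate. 4 × 150/24 = 25.0 days and 5 × 150/24 = 31.25 days. Days 28 and 35 are 28 × 24/150 = 4.48 and 35 × 24/150 = 5.60 half-lives. They would be exactly 4 and 5 only at a half-life of 168 h.

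**Fraction of steady-state trough (%).**

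| Half-life | Day 7 | Day 14 | Day 21 | Day 28 | Day 35 | Day 35/28 |
|---|---|---|---|---|---|---|
| TFV-DP, 150 h | 54.0 | 78.8 | 90.3 | 95.5 | 97.9 | 1.025 |
| TFV-DP, 225 h (150 × 1.50) | 40.4 | 64.5 | 78.8 | 87.4 | 92.5 | 1.058 |
| TFV-DP, 247.5 h (150 × 1.65) | 37.5 | 61.0 | 75.6 | 84.8 | 90.5 | 1.067 |
| FTC-TP, 36 h | 96.1 | 99.8 | 100.0 | 100.0 | 100.0 | 1.000 |

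Serum TFV and FTC are above 99% by Day 7. At 150 h the expected TFV-DP rises are 46% (Day 7 to 14), 14.5% (14 to 21), 5.8% (21 to 28) and 2.5% (28 to 35).

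**Can the plateau be extrapolated from three days?** Within one participant, let r = (y21 - y14)/(y14 - y7). The plateau is y7 + (y14 - y7)/(1 - r), defined only for 0 < r < 1. In simulation at 150 h, with assumed within-person CVs of 5%, 10%, 20% and 30%, a plateau could be computed in 89%, 59%, 32% and 23% of participants. At 10%, the 5th to 95th percentiles of the estimates run from 0.81 to 3.05 times the true plateau.

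**Effect of drift on the CV.** For two values a and b, the drift-only CV is √2(b - a)/(a + b).

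- 150 h: 1.414 × (97.9 - 95.5)/193.4 = 1.8%.
- 225 h: 1.414 × 5.1/179.9 = 4.0%.
- 247.5 h: 1.414 × 5.7/175.3 = 4.6%.

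Added in quadrature to a 20% CV: √(20² + 1.8²) = 20.1% and √(20² + 4.6²) = 20.5%. Added to a 10% CV at the longest half-life: √(10² + 4.6²) = 11.0%.

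**Precision of a direct check.** A 20% CV is a log-scale SD of √ln(1.04) = 0.198. The 90% half-width for the mean log ratio is:

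- pooled, 32 pairs: 1.696 × √2 × 0.198/√32 = 0.084, about -8% to +9%;
- one arm, 8 pairs: 1.895 × √2 × 0.198/√8 = 0.19, about -17% to +21%.

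**The case against.** Several points on the other side stand.

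- **Only TFV-DP is affected.** Section 7.6.1.2 covers all analytes in blood and blood cells. FTC-TP ("given its far shorter 36-hour half-life") and serum TFV and FTC are at or near plateau by Days 7 to 14, so for them the stated days are informative.
- **Days 7 to 21 carry some information on TFV-DP.** They inform the accumulation rate, and a rate implies the fraction reached by Day 28. That is weak in one person but better at arm or study level.
- **A charitable reading exists.** The early days may be meant as the approach to Days 28 and 35, viewed together. That would be a sound check, but the sentence does not say it.
- **The drift is disclosed.** Section 1.2.3 states it, compares it with assay variation and explains the trade-off against longer dosing. The Figure 1-1 caption also points to it.
- **A direct check has limits.** The pooled interval is wider than every drift in the table, and a by-arm ratio is too imprecise to be useful.

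A reader might infer that the half-life mapping in section 1.2.3 undermines Days 28 and 35. It does the opposite. At 150 h those days are later than 4 and 5 half-lives, and the expected drift is 2.5% rather than 4%. A reader might also infer that the variability objective is seriously biased. The figures above do not support that.

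The point is not a complaint about detail left to an analysis plan. The protocol fixes a specific check on specific days, and for TFV-DP those days cannot serve it.

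**Conclusion.** For TFV-DP, the check stated in section 7.6.1.2 cannot do what it claims. Days 7, 14 and 21 lie at about 54%, 79% and 90% of steady state and, by the protocol's own labels, describe accumulation. By themselves they cannot confirm that Days 28 and 35 are at steady state. FTC-TP and serum TFV and FTC are outside the point.

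The expected numerical consequence is small. Drift alone gives a CV of about 1.8% for a typical participant and 4.0% to 4.6% at one SD longer half-life, which moves a 20% CV by about half a point at most. The correction is worth making because it costs almost nothing and replaces a rule that does not work. It does not put the objective at risk.

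This rests on first-order accumulation, the 150 h half-life, reading the 50% to 65% CV as applying to half-life (the protocol quotes it jointly with peak concentration), and the assumed within-person CVs of 5% to 30%.

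**What to change.** In section 7.6.1.2:

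- For TFV-DP, judge steady state from the trough trend through Days 21, 28 and 35. Day 21 is there to show the rises shrinking (5.8%, then 2.5% expected), not as a plateau point.
- Report the Day 35/Day 28 geometric mean ratio with a 90% CI, pooled across arms, and say that at this sample size it can exclude only large average drift.
- Read it alongside the individual Day 35 to Day 49 half-lives already planned in section 7.6.2.1, which identify slow eliminators that an average ratio would miss.
- Estimate the within-person CV with a day effect, so that mean drift is not counted as variability. Drift peculiar to slow eliminators will remain, at the size shown above.
- Keep Days 7, 14 and 21 for the accumulation rate.

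As a minor correction, section 1.2.3 should say that at 150 h Days 28 and 35 are about 4.5 and 5.6 half-lives (95.5% and 97.9% of steady state, drift about 2.5%).

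The cost is one rewritten paragraph and a small extra model on samples already scheduled. No visit, sample or dosing changes.

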**Table 1-1. Accumulation index for parent and phosphorylated moieties of TDF and FTC dosed either weekly (168 hours) or daily (24 hours).** Drug moieties and regimens are ranked by accumulation index. An index of 2 indicates a doubling of concentration at steady-state compared to a single dose. An index of 1 indicates no accumulation at steady-state. For example, the concentration observed with 100% adherence can look the same as no adherence if the non-adherent participant takes a single dose prior to the observed blood collection when TFV, FTC or TDF/FTC are used with prescribed weekly dosing regimens. By contrast, the concentration expected with 100% adherence to Truvada® will be 9.6 (TFV-DP) or 2.7 (FTC-TP) times the concentration observed if a participant has taken only a single dose prior to the scheduled observation. (Hawkins et al., 2005; Pruvost et al., 2005; Pruvost et al., 2009; Wang et al., 2004)

Drug moiety	Half-life (hours)	Dosing interval (hours, tau)	Dosing interval / half-life (tau/HL)	Accumulation index (Rac)
TFV-DP	150	24	0.2	9.5
FTC-TP	36	24	0.7	2.7
TFV-DP	150	168	1.1	1.9
TFV	17	24	1.4	1.6
FTC	10	24	2.4	1.2
FTC-TP	36	168	4.7	1.0
TFV	17	168	9.9	1.0
FTC	10	168	16.8	1.0

For this reason, TFV-DP (the intracellular form of TFV) is an excellent candidate for drug adherence monitoring, especially with daily dosing (Table 1-1). With an intracellular half-life of 150 hours, daily to weekly dosing of TDF has a TFV-DP accumulation index ranging from 9.5 to 1.9, offering a great range of sensitivity for determining reduced adherence over a large range of dose frequencies. In contrast, TFV concentration (measured in blood serum), when TDF is dosed daily, would be expected to perform much less well, with a small difference in drug accumulation at steady-state during daily dosing when compared to a single dose (e.g., taken on the day of observation). When using TDF on a weekly dosing regimen, there is no anticipated difference between drug concentrations of serum TFV compared to taking a single dose of TDF without any prior doses. Contrasting Figure 1-1 with Figure 1-2 illustrates this point graphically. The different dose regimens are easily distinguishable in Figure 1 where intracellular TFV-DP is measured. In contrast, the TFV serum levels are largely overlapping with daily and weekly dosing at least one day per week.

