#### **4.5.2 Dose Modification**

No dose modifications are permitted.

If absolutely necessary, dosing may be delayed for 2 days in Arms 1-3 during the first 3 weeks on study. Thereafter, all doses in week 4 and 5 must be taken as scheduled. All doses for research participants in Arm 4 must be taken as scheduled. Failure to comply with these schedule requirements will result in termination of the participant from the protocol after a final safety evaluation.

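### Section 7.6.1.2 bases the accumulation rate constant on Days 7, 14 and 21 only, which cannot identify k for FTC-TP and needlessly cost precision for TFV-DP

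*Protocol*

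**What the plan says.** Protocol section 7.6.1.2 describes intra-participant variability from Days 28 and 35, checks steady state with Days 7, 14 and 21, and then adds, as supportive evidence, that "the accumulation data from Day 7, 14, and 21 will also be used to estimate the elimination rate constant". It names no analyte for this estimate and does not say whether it is made per participant or pooled.

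The half-lives are in section 1.2.3: "Based on an estimated 150-hour TFV-DP intracellular half-life" and, for the other analyte, "FTC-TP will achieve steady-state earlier, given its far shorter 36-hour half-life".

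Other sections tie more samples to accumulation. Section 2.3.2 lists Enrollment and Days 7, 14, 21, 28 and 35 for the rate of accumulation. Section 5.0 schedules pre-dose #2 as the accumulation-index draw: Day 1 in Arm 4, Day 3 in Arms 2 and 3, Day 7 in Arm 1. Section 7.6 never uses pre-dose #2.

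The main elimination rate constant is a different estimate: section 7.6.2.1 takes it from the decline between Day 35 and Day 49.

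**The concern.** An accumulation curve carries information on k only where the level still depends on k, relative to a plateau that must itself be estimated. If the first sample is already at plateau, any k above some value fits equally well. For FTC-TP, Day 7 is 168/36 = 4.7 half-lives after the first dose, so the named days look too late. For TFV-DP they fall on the rise, but the plateau and the earliest rise are left out although both are sampled.

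Section 7.3 also lets a participant miss one of these three visits and remain evaluable, which leaves two points for two unknowns.

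At stake is a supporting estimate of k, and the use of a blood draw taken for accumulation that no analysis in section 7.6 uses.

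**Working it through.** **Inputs.** Half-lives T of 150 h and 36 h (section 1.2.3, Table 1-1); sampling days (sections 2.3.2 and 5.0); twice-weekly dosing on Monday and Thursday (Figure 1-1 legend). The only noise figure given is assay variation of more than twice a 4% difference, so above 8% (section 1.2.3). Total within-person CV is not given; I assume 10%, 15% and 25%, with log-scale SD σ = CV.

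**The protocol's own figures.** "Intracellular TFV-DP concentrations are estimated to achieve between 93% and 97% of steady-state" after 4 and 5 half-lives: 1 - 2^-4 = 93.75% and 1 - 2^-5 = 96.9%. "daily to weekly dosing of TDF has a TFV-DP accumulation index ranging from 9.5 to 1.9": 1/(1 - 2^(-24/150)) = 9.53 and 1/(1 - 2^(-168/150)) = 1.85. Both reproduce, so the first-order model is the protocol's own.

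**Fraction of plateau at weekly visits**, 1 - 2^(-24d/T), the same in every arm:

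| Analyte | Day 7 | Day 14 | Day 21 | Day 28 | Day 35 |
|---|---|---|---|---|---|
| FTC-TP | 96.1% | 99.8% | 99.99% | 100% | 100% |
| TFV-DP | 54.0% | 78.8% | 90.3% | 95.5% | 97.9% |

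FTC-TP has about 4% left to rise after Day 7, less than the assay variation. TFV-DP rises by 90.3/54.0 - 1 = 67% from Day 7 to Day 21.

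**Precision from Days 7, 14 and 21.** The model is log C = log Css + log(1 - e^(-x)), with x = ln2 × 24d/T. The sensitivity to log k is g = x e^(-x)/(1 - e^(-x)). With Css and k both unknown, the relative SE of k is c × σ, with c = 1/√Σ(g - mean g)².

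- FTC-TP: x = 3.235, 6.469, 9.704; g = 0.1326, 0.0100, 0.0006; Σ(g - mean)² = 0.01084; c = 9.60.
- TFV-DP: x = 0.776, 1.553, 2.329; g = 0.662, 0.417, 0.251; Σ(g - mean)² = 0.0852; c = 3.43.
- TFV-DP with Day 7 missed: c = √2/(0.417 - 0.251) = 8.5, or 85% even at CV 10%.

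**Other sample sets**, by the same calculation with the superposed dose schedule. Relative SE of k per participant, in %, at CV 10/15/25%:

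| Samples | FTC-TP c | FTC-TP | TFV-DP c | TFV-DP |
|---|---|---|---|---|
| Days 7, 14, 21, any arm | 9.604 | 96/144/240 | 3.426 | 34/51/86 |
| plus Days 28, 35 (all samples in Arm 1) | 8.583 | 86/129/215 | 2.144 | 21/32/54 |
| plus pre-dose #2 only, Arms 2-3 | 1.386 | 14/21/35 | 2.002 | 20/30/50 |
| plus pre-dose #2 only, Arm 4 | 1.542 | 15/23/39 | 1.909 | 19/29/48 |
| all, Arms 2-3 | 1.284 | 13/19/32 | 1.390 | 14/21/35 |
| all, Arm 4 | 1.425 | 14/21/36 | 1.345 | 13/20/34 |

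For FTC-TP nearly the whole gain comes from pre-dose #2. In Arm 1 that sample is the Day 7 sample, so nothing changes there.

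**Why pre-dose #2 helps FTC-TP.** In Arm 4, Day 1 is at 1 - 2^(-24/36) = 37% of plateau, on the rise. In Arms 2 and 3, Day 3 is at 2^(-72/36) = 0.250 of a dose. Day 7 is at 2^(-168/36) + 2^(-96/36) = 0.039 + 0.157 = 0.197, and the plateau trough is 0.197/0.961 = 0.205. There the sample lies above the plateau trough and informs k through the unequal 3- and 4-day gaps.

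**Simulation check** (least-squares fits, CV 15%, 5th-95th percentile of the fitted half-life):

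- FTC-TP, true 36 h: from the 2 h search bound to about 110 h on Days 7-21, against 25-51 h (Arm 4) and 26-50 h (Arms 2-3) with all samples.
- TFV-DP, true 150 h: about 62-476 h, against 107-213 h (Arms 2-4) and 85-254 h (Arm 1).

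**The case against.** The strongest reply is that the estimate is supportive and the main k comes from the Day 35-49 decay. That stands, and for TFV-DP the decay estimate is good. Over 336 h its relative SE is √2σ/(ln2 × 336/150) = 0.91σ, or 9-23% at CV 10-25%. For FTC-TP it helps less: 336 h is 9.3 half-lives, leaving 2^-9.3 = 0.16% of the Day 35 level. Whether that is measurable depends on an assay limit the protocol does not give.

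Second, the text does not require per-participant fits, nor say that Days 7-21 are the only samples allowed. A shared k across 32 participants has relative SE c × σ/√32, which is 6-15% for TFV-DP. This stands, and it defeats any claim that the TFV-DP estimate could not be compared with the decay result. Pooled FTC-TP is still 17-42%, and rests on a 4% difference that a 4% offset common to Day 7 would erase. Reading Days 28 and 35 into the rule improves TFV-DP to 21-54% but leaves FTC-TP at 86-215%.

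A reader might go further than the documents allow:

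- That TFV-DP is barely informative, with half-lives ranging over a factor of 20. Days 7-21 cover 54-90% of plateau. A range that wide needs per-participant fits and noise near 20%; at 10% the range is about 86-280 h.
- That serum TFV and FTC are affected. The sentence names no analyte, and section 7.6.2.1 defines the rate constant for the intracellular phosphates only.
- That delayed doses distort the estimate. Section 4.5.2 does say "If absolutely necessary, dosing may be delayed for 2 days in Arms 1-3 during the first 3 weeks on study", but nothing prescribes nominal times. Section 2.3.2 requires accurate sample times, and section 4.3.1 has dose date and time on the DOT log.

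**Conclusion.** The point holds in limited form. The sampling days fixed in section 7.6.1.2 cannot identify a participant's FTC-TP rate constant from accumulation (relative SE about 96-240%). They are usable but needlessly imprecise for TFV-DP (34-86%). The samples already drawn bring FTC-TP to 13-36% in Arms 2-4, and TFV-DP to 13-35% in Arms 2-4 and 21-54% in Arm 1. FTC-TP in Arm 1 remains unidentified whichever scheduled samples are used.

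The fractions of plateau follow from the protocol's half-lives. The standard errors also rest on first-order kinetics and the assumed CVs of 10-25%. They scale in proportion to the CV, so the comparison between sample sets does not depend on it.

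The rule is stated text at odds with sections 2.3.2 and 5.0, so it is more than detail left for an SAP. The consequence is modest: neither the dose-proportionality decision nor the Day 28/35 variability estimate uses this k.

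**What to change.** In section 7.6.1.2, replace the rule with this: the accumulation-based k for TFV-DP and FTC-TP is estimated from all on-treatment blood samples (pre-dose #2 and Days 7, 14, 21, 28 and 35) with a first-order superposition model, using recorded dose and sample times, per participant or pooled. Say which of the two is meant. State that FTC-TP k is not estimable from accumulation in Arm 1, where pre-dose #2 is the Day 7 sample.

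The cost is analysis wording only, since the samples are scheduled and the times recorded. The plan gives up an accumulation-based FTC-TP estimate in Arm 1, which the present rule cannot deliver either. In Arms 2 and 3 the FTC-TP estimate will lean on the superposition model, because pre-dose #2 there informs k through the unequal gaps; the report should say so.
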